**Figure 2: Dose Finding Rules Per BOIN**

## 3.2. Study Phase and Cohorts

### 3.2.1. Phase 1 Design

[figure not shown]
A BOIN design will be utilized to determine the MTD of NC525, where a minimum of 3 evaluable subjects will be enrolled at each level from Cohort 2 onwards. In the case of the starting dose level (2mg/kg), a minimum of 1 evaluable subject may be enrolled (in the absence of severe toxicity) prior to determining escalation to the next dose level given the dose is an approximation of the minimally active dose (PD30).

All dose escalation decisions will be based on the occurrence of DLTs at a given dose during the first 56-day period (i.e., first 2 cycles), also referred to as the DLT observation period (Figure 3). Dose escalation decisions will be made jointly by the Clinical Study Team comprised of the

[figure not shown]
Sponsor Medical Monitor, CRO Medical Monitor and Investigators once the minimum number of evaluable subjects (n=3) have completed the DLT observation period.

**Figure 3: Phase 1 Study Schema**

### a. Cohort 1

### **b. Cohort 2 and Above**

A subject is considered evaluable if they have received at least four doses of NC525 and completed the 56-day DLT observation period or discontinued earlier due to an adverse event. Only one subject will be dosed on the first day of dosing for each cohort (additional subjects can begin in  $\geq$  48 hours). If there are multiple subjects in the screening process at the time the third subject within a cohort begins treatment, additional subjects may be enrolled with approval of the Sponsor using the BOPIN design and based on the number of subjects evaluable at the current dose level.

The Escalation/De-escalation Rules per BOIN (Table 1) can be used to help inform decisions during the safety review meetings. Dosing decisions include escalate to the next higher dose, stay at the current dose, de-escalate to the next lower dose, or eliminate the dose level (i.e., unacceptably toxic dose). Dose escalation and de-escalation will be based on the cohort size of 3. That is, no dose escalation will be made before 3 patients are treated at the current dose, except the first dose where the accelerated titration may be performed and a minimum of 1 subject may be enrolled.

To reference the dose finding rules, one can use the number of evaluable subjects in a cohort that have been treated to determine the appropriate action based on the number of subjects who have experienced a DLT as indicated by the column. For example, at a given dose level, if 6 subjects have been enrolled but only 5 evaluable subjects have passed the 56-day DLT observation period, a decision could be made to escalate to the next dose cohort as long as there is  $\leq 1$  DLT in any of the 5 subjects.

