**Table 1: Dose escalation/de-escalation rule for the BOIN Design**

Escalation/De-escalation Rules														
Action**	Number of evaluable patients treated*													
	3	4	5	6	7	8	9	10	11	12	13	14	15	
Escalate if number of DLT $\leq$	0	0	0	1	1	1	1	1	2	2	2	2	2	2
Stay at current dose if number of DLT is equal to	1	1	1	NA	2	2	2	2	3	3	3	3	3, 4	3, 4
De-Escalate if the number of DLT $\geq$	2	2	2	2	3	3	3	3	4	4	4	5	5	5
Eliminate if number of DLT $\geq$	3	3	3	4	4	4	5	5	6	6	6	7	7	

Note. "# of DLT" is the number of subjects with at least 1 DLT. When none of the actions (i.e., escalate, de-escalate or eliminate) is triggered, stay at the current dose for treating the next cohort of subjects.

\*A subject is considered evaluable if they have received at least four doses of NC525 and completed the 56-day DLT observation period or discontinued earlier due to an adverse event.

\*\*If de-escalation rule is met at Dose Level 1, alternative dose levels or administration schedules may be considered pending safety review and emerging data.

In addition to the BOIN dose finding rules, decisions to escalate to the next dose will be based on all available PK, PD, efficacy, safety, and tolerability data for the prior cohort(s). Efficacy measures consist of MLFS, CR, CRh, CRi and hematological recovery. Since NC525 targets and effectively kills leukemic blasts and LSC, PD marker comprises clearance of blasts from the marrow and peripheral blood. Further PD marker such as expression of LAIR-1 on blast cells to correlate with response will be assessed.

Two dose levels will be expanded to determine an optimal Recommended Phase 2 Dose (RP2D) and administration schedule of NC525. After Dose Escalation has been completed, safety

expansion up to 14 subjects per dose (including subjects treated at that dose level in the dose escalation phase) will be performed.

The doses for safety expansion are required to be no higher than the MTD and show sufficient PK/PD and anti-leukemic activities. The RP2D will be chosen based on an overall assessment of DLTs, safety profile, subject tolerance, biological activities and clinical efficacy signals collected at all different doses tested. The RP2D is required to be no higher than the MTD. A Bayesian toxicity monitoring rule will be used to ensure safety during safety expansion. Refer to [Section 10.2.2](#) for details.

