#### **3.4.2. Replacement of Subjects**

Subjects may be replaced for any of the following reasons:

- If a subject withdraws from treatment before the completion of the DLT period for any reason other than a DLT (e.g., subject is not evaluable for DLTs)
- Subject does not meet the eligibility requirements of the study (accidental enrollment)

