## **5.9. Dose Limiting Toxicities (DLTs)**

### **5.9.1. Dose-Limiting Toxicity and Determination of Maximum Tolerated Dose**

During Dose Escalation, the evaluation period for DLTs will begin on Cycle 1 Day 1 and will continue up to 56 days. All DLTs will be assessed by the investigator using National Cancer Institute Common Terminology Criteria for Adverse Events (NCI CTCAE) v5.0. A DLT will be defined as the occurrence of any toxicity in [Table 6](#), except for events clearly associated with the underlying disease or an extraneous cause (e.g., car accident).

Individual subject dose reductions may be made based on events observed at any time during treatment with NC525; however, for the purposes of dose cohort escalation/de-escalation, and expanding a dose cohort, the decisions will be made based on events that are observed from the first day of study treatment through and including the 56-day DLT period. Alternative dose levels may subsequently be determined based on relevant toxicities that become evident after the 56-day DLT period.

**Table 6: Definition of Dose-Limiting Toxicity National Cancer Institute Common Terminology Criteria for Adverse Events (NCI CTCAE) v5.0**

Nonhematologic toxicity

Any grade 3 nausea, vomiting or diarrhea that requires TPN, tube feeding, or hospitalization is a DLT without exception

Any other grade 3 adverse reaction (including laboratory abnormalities) lasting more than 72 hours, with the following exceptions:

Grade 3 fatigue lasting >3 days

Any grade 4 nonhematological adverse reactions.

Any Hy's law case defined as:

Combined elevations in serum ALT >3 times the upper limit of normal (ULN) and bilirubin >2 ULN in the absence of alkaline phosphatase (ALP) elevation (<2 ULN). Note: Abnormal liver function tests as indicated by the criteria above will be considered a DLT if no other reason can be found to explain the combination of increased liver markers such as viral hepatitis A, B, or C; preexisting or acute liver disease; or another drug capable of causing the observed injury

Hematologic toxicity

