

Any grade >3 ANC or PLTS lasting more than 7 days is a DLT in the absence of active leukemia. Note: Patients with active leukemia are not evaluable for a hematological DLT.

General

Any infusion reaction that is not resolved within 24 hours.

Any adverse reaction that resulted in dose reduction or withdrawal.

Any fatal adverse reactions.

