## **5.10. Withdrawal/Discontinuation of Subjects from Study Treatment**

### **5.10.1. Withdrawal/Discontinuation Criteria**

Subjects may withdraw consent at any time for any reason or be removed from the trial at the discretion of the investigator should any untoward effect occur. In addition, a subject may be withdrawn by the investigator or the Sponsor if enrollment into the trial is inappropriate, the trial plan is violated, or for administrative and/or other safety reasons.

Discontinuation of study treatment does not represent withdrawal from the study. A subject may discontinue from treatment but agree to remain on-study, as long as the subject does not withdraw consent.

If a subject is withdrawn, then every reasonable effort should be made to determine the reason for withdrawal, and this information should be recorded in the electronic case report form (eCRF).

Subjects must be withdrawn from the trial for any of the following reasons:

- The subject is lost to follow-up
- Consent is withdrawn for study (does not agree to follow-up); no additional data collection should occur

Subjects must discontinue from the study treatment but can continue to be monitored for any of the following reasons:

- Consent is withdrawn for treatment (agrees to follow-up)
- The subject becomes pregnant
- Confirmed progressive disease (except if Sponsor approves treatment continuation)
- Unacceptable adverse experiences
- Investigator's decision to withdraw subject
- Subjects proceed to stem cell transplantation
- Discontinuation of treatment may be considered for subjects who have attained a confirmed CR, CRh, or CRi and have been treated for two years with NC525
- Any study intervention-related toxicity specified as a reason for permanent discontinuation as defined in the guidelines for dose modification due to AEs in [Section 5.8](#).
- The study is terminated by the IRB, regulatory authority, or Sponsor

Subjects who discontinue study treatment but agree to remain on-study should continue to be followed according to the applicable Post-Treatment Follow-up schedule. All subjects will be followed for overall survival (OS) until death, withdrawal of consent, or the end of the study.

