## **9. SAFETY MONITORING AND REPORTING**

### **9.1. Adverse Events (AEs)**

#### **9.1.1. Adverse Event Definition**

For the purposes of this protocol, an AE is defined as any untoward medical occurrence associated with the use of a drug in humans, whether considered drug related, that occurs after a subject provides informed consent and through the follow-up period. Both nonserious and serious AEs (SAEs) will be monitored throughout the study.

A pre-treatment event (PTE) is one that occurs after the time of informed consent (e.g., during the screening process) but prior to study drug administration. PTEs directly related to a study test or procedure should be reported during the Screening period.

Conditions that were already present at the time of informed consent should be recorded on the Medical History form in the eCRF.

Abnormal laboratory values or test results occurring after informed consent constitute AEs only if they induce clinical signs or symptoms, are considered clinically meaningful, require therapy (e.g., hematologic abnormality that requires transfusion), or require changes in the study drug(s).

Progression of the cancer under study is not considered an adverse event unless it results in hospitalization or death.

Hospitalization of a subject to allow for observation and management (e.g., IV hydration) for the purpose of TLS prophylaxis will not be captured as an SAE unless there is an additional reason for hospitalization or an additional criterion for seriousness other than hospitalization is met.

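### A subject who stops early for a disease-related or extraneous adverse event is DLT-evaluable under Section 3.2.1 and Table 1, but replaceable as not evaluable under Section 3.4.2

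*Combined protocol and SAP*

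**What the plan says.** **Who is evaluable.** Section 3.2.1 (under Cohort 2 and Above), the Table 1 footnote and their synopsis counterparts count a subject who has "received at least four doses of NC525 and completed the 56-day DLT observation period or discontinued earlier due to an adverse event". The cause of the adverse event is not restricted.

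**Who may be replaced.** Section 3.4.2 covers a subject who leaves treatment before the DLT period ends "for any reason other than a DLT (e.g., subject is not evaluable for DLTs").

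**What is a DLT.** Section 5.9.1 applies Table 6 "except for events clearly associated with the underlying disease or an extraneous cause". Table 6 itself includes "Any adverse reaction that resulted in dose reduction or withdrawal".

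**What is an adverse event.** Section 9.1.1 does not require a relationship to the drug. It adds: "Progression of the cancer under study is not considered an adverse event unless it results in hospitalization or death". Section 5.10.1 lists progression as a separate reason to stop treatment: "Confirmed progressive disease (except if Sponsor approves treatment continuation").

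**Where the count is used.** It selects the Table 1 column. It also enters step 3 of Section 10.2.1, which stops escalation when nine evaluable subjects are reached at a dose and the action is to stay, and the one-subject minimum at Dose Level 1 in Section 3.2.1.

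**The concern.** Take a subject who stops NC525 before Day 56 for an adverse event clearly due to the leukemia or to an outside cause, with no DLT. Section 3.2.1 and Table 1 put this subject in the denominator as DLT-free. Section 3.4.2 treats the subject as replaceable and, by its example, as not evaluable. Nothing ranks the two rules, and nothing says whether a replaced subject leaves the denominator. Two teams could therefore read different Table 1 columns from the same data.

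The group is narrow, because Table 6 already makes withdrawal for an adverse reaction a DLT. It need not be empty: progression leading to hospitalization or death is an adverse event, and Section 9.1.4 describes disease-related cytopenias as common, though it does not say that they lead to stopping. Because progression is also a stop reason of its own, whether a subject counts can depend on how the stop is recorded.

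Defining the MTD is part of a primary objective, and this count drives it.

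**Working it through.** **1. Table 1 boundaries.** The target rate is 0.25 (Section 10.2.1). Assuming the usual BOIN limits of 0.6 and 1.4 times target, the cut-offs are 0.1968 (escalate) and 0.2984 (de-escalate). Elimination is taken as Pr(p > 0.25 | data) > 0.95 under a Beta(1,1) prior. These reproduce every escalation and elimination entry for n = 3 to 15. De-escalation agrees except at n = 3, where the formula gives 1 and the table gives 2; the 3+3 nesting stated in Section 3.1 accounts for that. The table is taken as correct.

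**2. Adding one DLT-free subject.** Compare the action at x DLTs in n with x in n + 1, for n = 3 to 11 (Section 10.2.1 caps a cohort at 12).

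| Not counted | Action | Counted | Action |
|---|---|---|---|
| 1/5 | stay | 1/6 | escalate |
| 3/5 | eliminate | 3/6 | de-escalate |
| 2/6 | de-escalate | 2/7 | stay |
| 4/8 | eliminate | 4/9 | de-escalate |
| 2/10 | stay | 2/11 | escalate |
| 3/10 | de-escalate | 3/11 | stay |
| 5/10 | eliminate | 5/11 | de-escalate |

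That is 7 of 72 cells (4 + 5 + … + 12 = 72), all in the less cautious direction. The cells are unweighted, so this is not a frequency of altered decisions. In addition, 2/8 to 2/9 remains a stay but reaches nine, so step 3 ends escalation. The 1/5 row rests on Table 1 alone: the worked example in Section 3.2.1 already allows escalation with one DLT in five.

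**3. Chance of 0/3, which permits escalation.** Let p be the true DLT rate and f the fraction of the 56 days for which the third subject is observed. Under a constant hazard (an assumption), the chance is (1 − p)^(2 + f).

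For f: a weekly-dosed subject who stops after the fourth dose (Day 22) has 21 days elapsed, plus the 30 days of adverse-event reporting after cessation in Section 9.1.7. So f = (21 + 30)/56 = 51/56.

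| Third subject | p = 0.25 | p = 0.41 (a Table 14 rate) |
|---|---|---|
| Fully observed, f = 1 | 0.75^3 = 42.2% | 0.59^3 = 20.5% |
| Stops after Day 22 dose, f = 51/56 | 0.75^2.911 = 43.3% | 0.59^2.911 = 21.5% |
| No information, f = 0 (upper bound) | 0.75^2 = 56.3% | 0.59^2 = 34.8% |

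The last row would fit an early death or withdrawn consent. None of these shifts occurs if the subject is replaced and left out of the denominator.

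**4. The four-dose condition.** The definition has no brackets. Read as (four doses and completed) or stopped for an adverse event, it counts a stop after any number of doses. Read as four doses and (completed or stopped), it counts only stops after the fourth dose: Day 22 on the weekly schedule, Day 43 in Cohort 1 (doses on Days 1, 15, 29 and 43). The mismatch with Section 3.4.2 exists under both readings but is smaller under the second.

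**The case against.** **Follow-up continues after treatment stops.** A reader might infer that observation ends at the last dose, so that a subject stopping on Day 22 supplies 21 of 56 days and the chance of 0/3 rises to 0.75^2.375 = 50.5% (0.59^2.375 = 28.6%). The documents do not support this. Section 5.10.1 separates stopping treatment from leaving the study. Section 9.1.7 keeps adverse-event reporting open for 30 days. Section 9.1.3 makes an event meeting the DLT definition an event of clinical interest, collected for 90 days, or 30 if new cancer therapy starts. This objection stands, and it reduces the typical shift to about one percentage point. It does not cover death, withdrawn consent or the reduced drug exposure after stopping.

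**Section 3.4.2 is permissive.** It says that subjects may be replaced, so it could be read as applying only to those already non-evaluable. That softens the conflict but does not remove it: the example attaches non-evaluability to a class that includes subjects whom Table 1 counts. If both the subject and the replacement are counted, the denominator grows by two.

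**The completion wording.** Decisions are made "once the minimum number of evaluable subjects (n=3) have completed the DLT observation period". A reader might take this as a further contradictory rule. It governs timing, applies equally to subjects who stop for a DLT, and can be met by a subject off treatment but still followed. It is not a separate error.

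**DLTs after one to three doses.** The unbracketed sentence might suggest that these are dropped. Table 1 counts subjects with at least one DLT, Section 5.9.1 counts events from the first treatment day, and Section 3.4.2 exempts DLT stops from replacement. The intent to keep them is clear enough, though not stated outright.

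**Team review.** The team weighs all safety data, and the one-subject minimum at Dose Level 1 requires no severe toxicity. Both reduce the risk. Neither settles the denominator.

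**Conclusion.** The mismatch between the evaluable definition and the replacement rule is real and unreconciled, for early stops due to adverse events clearly caused by the disease or an extraneous factor. One such subject can move Table 1 to a less cautious action or bring on the stop at nine. At a true rate of 0.25, the chance of 0/3 moves from 42.2% to about 43% with the planned 30-day follow-up, and to no more than 56.3% if the subject contributes nothing. These figures rest on one such subject among three, and the middle one also on a constant hazard. The documents give no rate for these stops, so the overall effect on MTD selection cannot be stated. A general claim that every adverse-event stop dilutes the DLT rate would go too far, because withdrawal for an adverse reaction is itself a DLT. The point merits correction because the rule as written can give a wrong table action and the remedy is cheap.

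**What to change.** Reconcile Section 3.2.1, the Table 1 footnote, Section 3.4.2 and the matching synopsis text to one bracketed definition. Use it for Table 1, the stop at nine in Section 10.2.1 and the one-subject minimum at Dose Level 1. A subject is evaluable if:

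- (a) they had a DLT within the 56-day period, regardless of the number of doses received; or
- (b) they had no DLT, were observed for the full 56 days, and met the protocol's minimum dose count.

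A subject meeting neither is left out of the count and may be replaced, as Section 3.4.2 already allows. A subject who stops treatment but is followed to Day 56 with the minimum dose count met still counts, so information is not discarded.

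The sponsor should confirm how the existing four-dose minimum applies to each schedule: 4 doses are planned in 56 days in Cohort 1, and 8 in later cohorts. The completion wording in Section 3.2.1 and the synopsis should be aligned at the same time.

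The cost is wording and possibly a few replacements. If 5%, 10% or 20% of subjects were non-evaluable leavers (an assumed range), 30 evaluable subjects would need 30/0.95 = 31.6, 30/0.90 = 33.3 or 30/0.80 = 37.5, that is about 32, 34 or 38 enrolled.

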**Table 1: Dose escalation/de-escalation rule for the BOIN Design**

Escalation/De-escalation Rules														
Action**	Number of evaluable patients treated*													
	3	4	5	6	7	8	9	10	11	12	13	14	15	
Escalate if number of DLT $\leq$	0	0	0	1	1	1	1	1	2	2	2	2	2	2
Stay at current dose if number of DLT is equal to	1	1	1	NA	2	2	2	2	3	3	3	3	3, 4	3, 4
De-Escalate if the number of DLT $\geq$	2	2	2	2	3	3	3	3	4	4	4	5	5	5
Eliminate if number of DLT $\geq$	3	3	3	4	4	4	5	5	6	6	6	7	7	

Note. "# of DLT" is the number of subjects with at least 1 DLT. When none of the actions (i.e., escalate, de-escalate or eliminate) is triggered, stay at the current dose for treating the next cohort of subjects.

\*A subject is considered evaluable if they have received at least four doses of NC525 and completed the 56-day DLT observation period or discontinued earlier due to an adverse event.

\*\*If de-escalation rule is met at Dose Level 1, alternative dose levels or administration schedules may be considered pending safety review and emerging data.

In addition to the BOIN dose finding rules, decisions to escalate to the next dose will be based on all available PK, PD, efficacy, safety, and tolerability data for the prior cohort(s). Efficacy measures consist of MLFS, CR, CRh, CRi and hematological recovery. Since NC525 targets and effectively kills leukemic blasts and LSC, PD marker comprises clearance of blasts from the marrow and peripheral blood. Further PD marker such as expression of LAIR-1 on blast cells to correlate with response will be assessed.

Two dose levels will be expanded to determine an optimal Recommended Phase 2 Dose (RP2D) and administration schedule of NC525. After Dose Escalation has been completed, safety

expansion up to 14 subjects per dose (including subjects treated at that dose level in the dose escalation phase) will be performed.

The doses for safety expansion are required to be no higher than the MTD and show sufficient PK/PD and anti-leukemic activities. The RP2D will be chosen based on an overall assessment of DLTs, safety profile, subject tolerance, biological activities and clinical efficacy signals collected at all different doses tested. The RP2D is required to be no higher than the MTD. A Bayesian toxicity monitoring rule will be used to ensure safety during safety expansion. Refer to [Section 10.2.2](#) for details.

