### **5.8. Dose Modifications**

#### **5.8.1. Criteria and Procedures for Modifications, Dose Interruptions and Adjustments of Study Treatments**

Treatment with NC525 may be delayed allowing for resolution of toxicities. Subjects may resume treatment if no medical condition or other circumstance exists that, in the opinion of the investigator, would make the subject unsuitable for further participation in the study.

For Cohort 1, NC525 is given by Intravenous (IV) infusion every two weeks (on Days 1 and 15 of each cycle) for the first 6 cycles. For subjects who continue on treatment beyond Cycle 6, NC525 will be administered every 4 weeks (on Day 1 of each cycle only).

For Cohort 2 and above, there are four doses per cycle when following the weekly (QW) dosing schedule. Cycles begin with the first dose of each cycle and no sooner than 7 days from the last dose of the prior cycle. Subjects may continue weekly (QW) dosing until overall response (e.g., CR, CRh, or CRi) is achieved, at which time they may switch to biweekly (Q2W) dosing. For subjects who achieve overall response and switch to a biweekly (Q2W) dosing schedule, there are two doses per cycle, cycles begin with the first dose of each cycle and no sooner than 14 days from the last dose of the prior cycle. Patients will be taken off study therapy if there is greater than a 14-day delay in scheduled treatment.

Cycles must be administered in consecutive order, and a cycle is never skipped even in the event of a delayed dose.

Study Treatment may be interrupted for situations other than treatment-related AEs such as medical or surgical events and/or unforeseen circumstances not related to study intervention. However, study intervention is to be restarted within 2 weeks or 14 days unless otherwise discussed with the Sponsor.

Individual decisions regarding dose interruptions should be made using appropriate clinical judgment in consultation with the medical monitor, considering relatedness of the AE to the study treatments and the subject's underlying condition. The Sponsor should be notified if a delay in study treatment is anticipated or occurs.

If study treatment is interrupted, the reason for interruption is to be documented in the subject's study record.

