**Table 4: Dose Modifications for Adverse Events**

AE Toxicity grade (CTCAE V5.0)	Action with NC525
Grade 3 Immune-related AE (e.g. pneumonitis, colitis, elevated LFTs (in absence of active disease), etc.)	Interrupt Treatment, Restart treatment at one dose level lower when the specific immune-related AE resolves to no more than Grade 1 in severity. If immune-related AE does not resolve in 14 days, or if the Grade 3 immune-related AE recurs, the subject must permanently discontinue.
Grade 4 Immune-related AE (e.g. pneumonitis, colitis, elevated LFTs (in absence of active disease), etc.)	Permanently Discontinue

AE Toxicity grade (CTCAE V5.0)	Action with NC525
Grade 3 or Grade 4 Tumor Lysis Syndrome (TLS)	
Interrupt Treatment, Restart treatment at the same dose when the TLS is resolved to no more than Grade 1 in severity within 2 weeks or 14 days,
 
For Management of TLS, see Appendix 5

Any Grade Infusion Reaction	See Table 5 for management of infusion reaction.
(Grading based on reporting of individual symptoms)	
Interrupt Treatment, Administer corticosteroids per standard of care. Restart treatment at the same dose level with the DS is resolved within 2 weeks or 14 days.

New Onset Grade 4 Neutrophil Count Decrease lasting > 1 week b	
Interrupt Treatment, Restart treatment at the same dose when the ANC is <math>\geq 500/\mu\text{L}</math> within 2 weeks or 14 days.
 
If Grade 4 neutropenia recurs, interrupt again but restart at one dose level lower when the ANC is <math>\geq 500/\mu\text{L}</math> within 2 weeks or 14 days.

New Onset Grade 4 Platelet Count Decrease lasting > 1 week b	
Interrupt Treatment, Restart treatment at the same dose when the platelet count <math>\geq 25,000/\mu\text{L}</math> within 2 weeks or 14 days.
 
If Grade 4 thrombocytopenia recurs, interrupt again but restart at one dose level lower when the platelet count is <math>\geq 25,000/\mu\text{L}</math> within 2 weeks or 14 days.

Any other non-hematological Grade 3 (other than TLS) adverse reaction	
Interrupt Treatment, Restart treatment at the same dose if the adverse reaction resolved to no more than Grade 1 in severity within 2 weeks or 14 days.
 
If the adverse reaction recurs at Grade 4, the subject must permanently discontinue.
 
If the adverse reaction recurs a second time at Grade 3, interrupt again, and the subject must permanently discontinue.

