### 7.3. Treatment Schedule

For Cohort 1, NC525 is given by Intravenous (IV) infusion every two weeks (on Days 1 and 15 of each cycle) for the first 6 cycles. For subjects who continue on treatment beyond Cycle 6, NC525 will be administered every 4 weeks (on Day 1 of each cycle only).

For Cohort 2 and above, NC525 will be administered every week on Days 1, 8, 15 and 22 during Cycles 1 and 2. Subjects may continue weekly dosing until overall response (e.g., CR, CRh, or CRI) is achieved, at which time they may switch to biweekly dosing. For biweekly dosing, NC525 will be administered every two weeks on Days 1 and 15 of each cycle. Subjects who derive clinical benefit may continue to receive NC525 for a total of 2 years or until the criteria for discontinuation of treatment are met (whichever comes first). A detailed description of the dosing schedule is included below ([Table 11](#)):

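### The four-dose DLT-evaluability threshold is all planned doses in Cohort 1 but only half in the weekly cohorts, and nothing says that a subject with a DLT always counts

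*Combined protocol and SAP*

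**What the plan says.** The evaluability definition appears in four places: the synopsis text on Cohort 2 and above, the footnote to Table S1, the matching text in Section 3.2.1, and the footnote to Table 1. A subject counts who has "received at least four doses of NC525 and completed the 56-day DLT observation period or discontinued earlier due to an adverse event". The columns of Table 1 are numbers of evaluable subjects.

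The window is the "first 56-day period (i.e., first 2 cycles), also referred to as the DLT observation period" (Section 3.2.1). Under Section 7.3, Cohort 1 is dosed "every two weeks (on Days 1 and 15 of each cycle) for the first 6 cycles", and Cohort 2 and above "every week on Days 1, 8, 15 and 22 during Cycles 1 and 2". Section 5.8.1 confirms that "there are four doses per cycle when following the weekly (QW) dosing schedule".

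Four other provisions bear on who counts:
- Section 5.8.1 tolerates delays up to a limit: "Patients will be taken off study therapy if there is greater than a 14-day delay in scheduled treatment".
- Table 4, for other non-hematological Grade 3 reactions, allows a subject to go on: "Restart treatment at the same dose if the adverse reaction resolved to no more than Grade 1 in severity", within 14 days. Table 6 makes most such reactions DLTs if they last more than 72 hours.
- Section 3.4.2 permits, but does not require, replacement of a subject who leaves treatment before the DLT period ends for a reason other than a DLT. It gives such a subject as an example of someone not evaluable.
- Section 5.10.1 lets a subject stop treatment and stay on study.

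**The concern.** A fixed count of doses means different things under the two schedules. In the weekly cohorts, a subject can satisfy it with half of the exposure that the DLT window is meant to test and still weigh as much in Table 1 as a subject who took every dose. If DLT risk grows with dosing, such subjects dilute the DLT count. That count steers escalation, the MTD is chosen from the same data (Section 10.2.2), and the MTD caps the RP2D.

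The definition can also err in the other direction. It rests on doses, time and discontinuation, and never on whether a DLT occurred. A subject with a DLT who resumes treatment but has too few doses could be left out of the denominator.

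**Working it through.** **Plan's own figures.** The documents do not print the interval cut-offs behind Table 1. Assuming 0.6 and 1.4 times the 25% target, the boundaries are 0.197 (escalate) and 0.298 (de-escalate). With elimination when the posterior probability of a DLT rate above 0.25 exceeds 0.95 under a Beta(1,1) prior, every column from n = 3 to 15 is reproduced. The one exception is de-escalation at n = 3: the plain rule gives 1, and the nested 3+3 rule stated in Section 3.1 gives the printed 2. The table is sound; the question is who enters it.

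**Planned doses in 56 days (Section 7.3).**
- Cohort 1: Days 1, 15, 29, 43 = 4 doses. Threshold 4/4 = 100%.
- Cohorts 2 to 6: Days 1, 8, 15, 22, 29, 36, 43, 50 = 8 doses. Threshold 4/8 = 50%, reached on Day 22.

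**Routes to half exposure without a DLT (weekly).** Assume that a delay pushes all later doses back.
- Delays: dose 5 is planned for Day 29. Two 14-day delays before it give 29 + 28 = Day 57, so four doses fall within 56 days. One 14-day delay leaves six. Table 6 does not list a delay by itself as a DLT.
- Stopping: a subject who stops after Day 22 for a reason other than an adverse event, such as transplantation (Section 5.10.1), can be observed to Day 56. Section 5.9.1 counts the DLT period in days from the first dose and does not require continued dosing.

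**A subject with a DLT and fewer than four doses.**
- Cohort 1, nominal calendar: dose 4 is due on Day 43. A 13-day delay gives Day 56, inside the window. A 14-day delay gives Day 57, leaving three doses inside.
- If the biweekly windows (+7 days at cycle start, +1 day at Day 15) apply and are fully used, dose 4 falls on 43 + 8 = Day 51, and a delay of 6 days is enough (Day 57).
- Such a subject who resumed treatment meets neither limb, if the four doses must fall within the 56 days. The text does not say whether they must.
- The and/or is unbracketed. Read as (four doses and 56 days) or discontinued, a subject stopped by an adverse event counts. Read as four doses and (56 days or discontinued), a subject stopped by a DLT before the fourth dose does not, in any cohort.
- Effect if such a subject is left out and a DLT-free subject takes the place: by Table 1, 1/3 (stay) becomes 0/3 (escalate), and 2/6 (de-escalate) becomes 1/6 (escalate).

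**Illustrative effect of half exposure.** Let p be the true eight-dose DLT risk. Under constant risk per dose, the four-dose risk is 1 − (1 − p)^(4/8). With k of three subjects at four doses, P(0/3) = (1 − p)^(3 − k) × (1 − p)^(k/2).

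| True p | Four-dose risk | P(0/3), k = 0 | k = 1 | k = 3 |
|---|---|---|---|---|
| 0.25 (target) | 13.4% | 0.75³ = 42.2% | 0.75² × 0.866 = 48.7% | 0.866³ = 65.0% |
| 0.41 (dose level 2, Scenario 1, Table 14) | 23.2% | 0.59³ = 20.5% | 0.59² × 0.768 = 26.7% | 0.768³ = 45.3% |

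For k = 3, the range over DLT timing runs from no change (all DLTs within the first four doses) to P(0/3) = 100% (all within the last four).

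**The case against.** The strongest reply is that other provisions already catch most of these cases, and much of it stands.

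- A reader might infer that in Cohort 1, where one subject can decide escalation, leaving out a subject with a DLT removes the deciding event. The documents do not support that. Step 1 in Section 10.2.1 adds two subjects at dose level 1 after any observed DLT, without reference to evaluability. Section 3.2.1 allows one-subject escalation only with an evaluable subject and no severe toxicity. The increment limits in Section 3.2.2 also respond to DLTs as such.
- The note to Table 1 counts subjects with at least one DLT, so the event may stay in the numerator. Section 3.4.2 does not provide for replacing a continuing subject who had a DLT. The denominator remains undefined, but a lost DLT is not the plan's evident intention.
- Half exposure by delay takes about two maximum delays. If adverse reactions cause them, many such subjects will already have a DLT under Table 6, which includes reactions leading to dose reduction or withdrawal. What remains is mainly non-toxicity stops and shorter, lower-grade interruptions.
- Section 3.4.2 regards the early non-DLT withdrawer as not evaluable. That helps, but replacement is optional, delays are not covered, and the statement conflicts with the Table 1 footnote for a subject who took four weekly doses.
- Table 1 only informs decisions; the study team also weighs all available PK, PD, safety and efficacy data. Under-dosing need not go unnoticed, but no listing of doses received is required.
- Timing is open. Systemic exposure in monkeys rose about 2-fold on repeated weekly dosing (Section 1.1.2), which leaves room for late toxicity. The named events of interest, including infusion reactions and tumor lysis, and the hospital stay of up to 48 hours after the first dose suggest that early risk is at least as plausible.

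**Conclusion.** The point holds as a defect of definition. The 100% versus 50% contrast is exact, and under the Table 1 footnote a weekly subject with four of eight doses and no DLT can count in full. The conflict with Section 3.4.2, the ambiguous and/or, and the missing clause for subjects with a DLT can all be read directly from the text.

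The size is conditional. At a true rate of 25%, the chance of 0/3 rises from 42% to 49% with one half-exposed subject and to 65% with three. Those figures assume constant risk per dose; the documents give neither the timing of DLTs nor the share of half-exposed subjects. The 65% is the case in which all three are half-exposed, not an expected value. A reader might infer that every weekly cohort will understate toxicity. That follows only if such subjects occur and some DLT risk lies in the later doses. The Cohort 1 case is narrow: about a 14-day delay, or less if visit windows are used.

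This should be fixed, because the definition feeds the trial's primary outputs and is cheap to repair. It does not invalidate the design.

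**What to change.** In the four places that carry the definition (synopsis text, Table S1, Section 3.2.1 text, Table 1):

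1. For subjects without a DLT, replace the fixed count with a common prespecified fraction of the doses planned in the 56-day window for the cohort's schedule, and say that doses are counted within that window. The sponsor should set the fraction. As an example only, 75% means 3 of 4 in Cohort 1 and 6 of 8 in the weekly cohorts; this would relax the present Cohort 1 requirement.
2. State that any treated subject with a DLT in the window is evaluable, whatever the number of doses. Write the remaining conditions so that the and/or can be read in one way only.
3. Reconcile Section 3.4.2 with the result, so that the same subject is not evaluable in one section and not evaluable in another, and say how subjects with delayed doses are handled.
4. List doses received and planned for each subject at every safety review (Section 9.5).

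The cost is a few sentences and perhaps some more replaced subjects in the weekly cohorts. Dosing does not change.
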